1.6. Confidentiality

The investigators, the designated CRO, other third-party vendors and Heel will preserve the confidentiality of all patients taking part in the study, in accordance with ICH GCP and local regulations. The confidentiality of all patient identities will be maintained except during source data verification, when monitors, auditors, and other authorised agents of the sponsor or its designee, the ethics committees approving this research, as well as any other applicable regulatory authorities, will be granted direct access to the study patients' original medical records. No material bearing a patient's name will be kept on file by the designated CRO, other third-party vendors or Heel. The data retained from this study will be protected in accordance with all applicable legal requirements.

Lateral ankle sprains are the most prevalent musculoskeletal injury in physically active populations. They also have a high prevalence in the general population and pose a substantial healthcare burden. The injury mechanism is characterised by a high velocity inversion and internal rotation of the ankle/foot complex. The treatment for acute lateral ankle sprain is quite variable, with many patients returning to activity in a short period of time; however, half of the population may never seek initial care (Gribble et al. 2016). Inadequate treatment of ankle sprains can lead to chronic problems such as decreased range of motion, pain, and joint instability (Wolfe et al. 2001; Ivins et al. 2006).

Many patients who suffer from some form of ankle injury do not seek treatment, as a treatment regimen would significantly impact their physical activities, such as training, practicing and competing for a substantial period of time (McKay et al. 2001). A study (Hubbard et al. 2009) showed that natural recovery from ankle sprain takes longer than 8 weeks – a significant time for any athlete to be away from activity.

Some evidence suggests that previous injuries or limited joint flexibility may contribute to ankle sprains. The initial assessment of an acute ankle injury should include questions about the timing and mechanism of the injury. Ankle sprains can be classified as grade 1, grade 2 or grade 3, depending on the severity of the injury (Wexler et al. 1998).

Physicians should apply e.g. the Ottawa ankle rules to determine whether radiography is needed. According to the Ottawa criteria, radiography is indicated if there is pain in the malleolar or midfoot zone, and either bone tenderness over an area of potential fracture (i.e. lateral malleolus, medial malleolus, base of fifth metatarsal, or navicular bone) or an inability to bear weight for four steps immediately after the injury and in the emergency department or physician's office (Tiemstra, 2012).

Clinically, a first approach to soft tissue injuries follows the RICE principle (simultaneous combination of all 4 elements Rest, Ice, Compression and Elevation). The objective of RICE is to stop the injury-induced bleeding into the muscle tissue and thereby minimize the extent of the injury.

In a study in acute ankle sprain, an accelerated intervention with early therapeutic exercise during the first week after ankle sprain improved ankle function compared with RICE, although the groups did not differ at any other time point for pain at rest, pain on activity, or swelling (Bleakley et al. 2010).

Controlled trials of non-steroidal anti-inflammatory drugs (NSAIDs) e.g. diclofenac, piroxicam, celecoxib, naproxen and others in patients with ankle sprain showed that compared with placebo, NSAIDs were associated with improved pain control and function, decreased swelling, and more rapid return to activity. To reduce or even avoid the well-known side effects of systemic NSAIDs topical application is an efficacious alternative (Lin et al. 2004, Mason et al. 2001, Mason et al. 2004, Heumann Pharma, Predel et al. 2004).

Reviews of diclofenac have consistently demonstrated its efficacy in reducing pain and inflammation in acute and chronic conditions compared with placebo. Diclofenac is meanwhile considered to be the gold standard in the treatment of joint sprains and other conditions. Topical diclofenac is well tolerated and is associated with fewer side-effects than other topical NSAIDs, mostly mild, easily resolved local skin irritation (Banning 2008, Zacher et al. 2008, Simon et al. 2009). A systematic review and meta-analysis of blinded, randomized, placebo-, vehicle- or active-controlled trials concluded that topical diclofenac appears to be generally well tolerated for cutaneous use in acute and chronic musculoskeletal conditions (Taylor et al. 2011). For these reasons, diclofenac gel was chosen as a comparator for this study.

Traumeel[®] is a German non-prescription drug sold for more than 50 years over the counter in pharmacies in Germany, Austria, Switzerland and in more than 50 other countries worldwide in the form of oral drops, tablets, ointment and ampoules. A gel formulation of the product is available in Austria, Belgium, The Netherlands, Poland and Spain in the EU, and in some other countries worldwide for human use as Traumeel[®] gel. In Germany the gel variant of the product is planned to be submitted for authorisation as Traumed[®] gel.

Traumeel[®] (for topical application, either as ointment or a gel) is produced in accordance with the German Homeopathic Pharmacopoeia and the European Pharmacopoeia. The quality of Traumed[®] is guaranteed both by the use of active substances and excipients that meet the requirements of the Homeopathic Pharmacopoeia and the European Pharmacopoeia and by production in accordance with good manufacturing practice (GMP) guidelines. Local tolerability data of Traumeel[®] gel are available from a local tolerability trial. Traumeel[®] is a fixed combination of plant and mineral extracts used for treating inflammation and pain caused by musculoskeletal injuries (Schneider, 2011). Efficacy and tolerability of Traumeel[®] for musculoskeletal injuries have been reported in randomised controlled trials, which demonstrate reductions in pain and swelling, and improvements in the mobility of joints such as ankle and knee (Zell et al. 1998, Böhmer et al. 1992, Thiel et al. 1994). Traumeel[®] has proven efficacy which is equivalent to conventional management (Schneider et al. 2008), NSAIDs (Birnesser et al. 2004) and to diclofenac (Schneider et al. 2005) in pain relief and improving joint mobility. Traumeel[®] is well tolerated, with very few adverse effects (Arora et al 2000, Birnesser et al. 2004, Böhmer et al. 1992, Thiel et al. 1994, Schneider et al. 2005. Schneider et al. 2008, Zenner et al. 1992, Zenner et al. 1994, Zenner et al. 1997).

Evidence for the inflammation regulating action of Traumeel® comes from Porozov et al. 2004 who conducted a study to evaluate the effect of Traumeel® on human leukocyte function. Specifically, the action of Traumeel® was studied on activated human T-cells, monocytes and gut epithelial cells in terms of its effect on the pro-inflammatory mediators IL-1 β (interleukin-1 β), TNF- α (tumour necrosis factor- α) and IL-8 (interleukin-8) *in vitro*.

The researchers found that Traumeel® modulates the secretion of IL-1 β , TNF- α and IL-8 in resting as well as in activated immune cells. It was observed that T-cell and monocyte proliferation was not affected. The researchers concluded that Traumeel® reduces pro-inflammatory cytokines in resting and activated immunocytes *in vitro*, as well as in resting and activated colon epithelial cells, suggesting that the first-line and mobile arm of immune defence is activated by Traumeel®. The study concluded that the results support the characterization of Traumeel® as an inflammation-regulating medication.

Traumeel® acts differently to NSAIDs, its anti-inflammatory effect results from the synergistic interaction between its components on the different phases of the inflammatory response (Lussignoli et al. 1999).

In vitro studies (Wexler et al. 1998) showed that the ingredients of Traumeel® are non-cytotoxic to granulocytes, lymphocytes, platelets and endothelial cells, indicating that the normal defensive and homeostatic functions of these cells are preserved during treatment with Traumeel®. Additional data alluding to the mode of action of Traumeel® comes from basic research (Heine et al. 2002) which has shown that the organic components of Traumeel® stimulate lymphocytes to synthesize and secrete the cytokine TGF- β (transforming growth factor- β) in whole blood cultures. TGF- β reduces pro-inflammatory substances such as TNF- α , Interferon-gamma, IL-1 and IL-2.

Traumeel® seems to modulate the healing process to assist resolution of symptoms including pain.

For homeopathic substances, pharmacokinetic investigations are not relevant regarding the efficacy of a substance or a combination of different substances. An expert's opinion on toxicology states that the material available and clinical experience provides no indication of toxicological risks associated with ingredients of the homeopathic drug Traumeel® when the product is applied as recommended.

A Traumeel® ointment and gel non-inferiority study (TAASS; Gonzalez et al. 2013) was conducted in 449 athletes with grade 1 or grade 2 acute ankle sprain as a multi-centre, randomized, blinded, parallel-group, active controlled study.

The baseline medians of the pain Visual Analog Scale (VAS) scale were lying between 52.6 mm and 55.7 mm (minimum 29.9 mm, maximum 94.8 mm). All groups showed strong pain decrease with a final median of 0 mm (total pain relief) after 6 weeks. At the

primary endpoint day 7 the median was 21.6 (Traumeel® ointment), 16.0 (Traumeel® Gel) and 17.5 (diclofenac gel).

Total pain relief at day 7 (-100.0%) was reached in 8.5% of the patients in the Traumeel® ointment group, in 5.0% of the patients in the Traumeel® gel group and in 5.9% of the patients in the diclofenac gel group.

The baseline medians of the Foot and Ankle Ability Measure (FAAM) Activities of daily living (ALD) score were lying between 51.2 and 56.0 (minimum 2.4, maximum 98.3). All groups showed strong increase of FAAM-ADL with a final median of 100 (best score) after 6 weeks. At the primary endpoint day 7 the median was 81.0 (Traumeel® ointment), 85.1 (Traumeel® gel) and 79.8 (diclofenac gel). Thus, the best median score was observed in the Traumeel® gel group, followed by the Traumeel® ointment group and the diclofenac gel group.

Altogether, 31 out of 447 patients of the safety population (6.9%) suffered from 43 AEs. At least one AE was experienced by 9 patients out of 152 patients (5.9%) of the Traumeel® ointment group, by 14 patients out of 148 patients (9.5%) of the Traumeel® Gel group and by 8 patients out of 147 patients (5.4%) of the diclofenac gel group. The proportion of treated patients with AEs was therefore below 10% in all treatment groups. The most common AE was headache, reported in 13 cases. None of these 13 headaches was assessed by the investigator as “possible” or “probable” related to investigational medication. Serious AEs were experienced by no patient and in no treatment group. There were no serious or fatal AEs.

Pharmacovigilance data on Traumeel® Gel show 9 non-serious adverse reactions (ARs), assessed with “possible” or “probable” causal relationship to the treatment, in the time period between 01.01.2008 and 01.01.2016. Two of the cases reporting skin reactions were received from a clinical study (TRS-ESP/ TAASS - Study/ EudraCT number: 2008-007939-4). One case reported eye hypersensitivity symptoms and can be considered as an isolated case. The other cases related to hypersensitivity skin conditions, which are already listed in the respective label (allergic reactions). The units sold on Traumeel® gel during this period are 2.047.579 packages. Thus, the incidence ratio for the non-serious ADRs is 7 cases per 2.047.579 packages, which means an event rate of 1 : 292.511.

No AEs indicative of Traumeel® overdose, either for ointment or gel, have been reported. Based on the available data, the overall safety profile of Traumeel® medications is considered being very good.

According to the SmPC of Diclofenac Heumann Gel (HEUMANN PHARMA GMBH & CO. GENERICA KG, N., 2013) its use is contraindicated in case of sensitivity to any components of the gel (e.g. paracetamol, isopropanol, ethanol; see section 6.1.1 for description of other ingredients), for patients in whom asthma attacks, skin rash or acute rhinitis are triggered by acetylsalicylic acid or NSAIDs, treatment for open wound,

infections or inflammation of the skin (e.g. eczema) or application on the mucosa. Possible side effects are also described in the SmPC.

Diclofenac Heumann Gel is only recommended in first and second trimester of pregnancy if absolutely required. Systemic administration of diclofenac inhibited the ovulation in rabbits and the implantation and embryogenesis in rats. Teratogenicity was investigated in rats, cats and rabbits. Based on the available non-clinical data, diclofenac is considered non-teratogenic. (HEUMANN PHARMA GMBH & CO. GENERICA KG, N., 2013).

Placebo is contraindicated in case of sensitivity to any components of the gel, see section 6.1.1 for description.

In the TAASS study (Gonzalez et al. 2013) topical treatment with Traumeel[®] or diclofenac resulted in reduction of pain and restoration of function in patients with grade 1 or grade 2 ankle sprain. The current study is designed to demonstrate the superior efficacy of Traumed[®] gel versus placebo and to assess the non-inferiority of Traumed[®] gel compared to diclofenac gel.

4. Study Objectives

The primary objective of the study is to demonstrate the superior efficacy of Traumed[®] gel versus placebo in patients with acute lateral ankle sprain.

The secondary objectives are:

- to assess the non-inferiority of Traumed[®] gel compared to diclofenac gel
- to assess the tolerability and safety of Traumed[®] gel.

5. Investigational Plan

5.1. Overall Design and Plan of the Study

This is a multicentre, double-blind, randomised, active- and placebo-controlled, parallel-group study.

After evaluation of entry criteria patients with grade 1 or 2 unilateral ankle sprain will be randomised to study treatment. The treatment will be 3 g of Traumed[®] gel or diclofenac gel or matching placebo gel, administered locally to sufficiently cover the area of the injury, 3 times daily for 7 days. The first treatment will be administered following the baseline study procedures and after randomisation of the patient on Day 1.

After end of investigational treatment patients will be followed up for another 7 days. Consequently, the entire duration of the study for each patient will be 14 days.

Patients will receive paracetamol (acetaminophen) 500 mg/tablet as rescue medication to be taken for pain relief when necessary (*pro re nata*, PRN) during the entire duration of the trial, see section 6.1.9 for further details. In addition, patients will not be allowed to take any pain relief medication other than the provided paracetamol, see section 6.2 for details.

All patients will receive soft support (elastic bandage) on Day 1. There will be a re-evaluation of grading of the disease at Day 4. Patients whose classification will be changed to Grade 3 will be withdrawn from the study. Grade 1 and grade 2 patients will continue using the soft support during the entire study, if required. Grade 2 patients will additionally receive a semi-rigid removable brace on Day 7, see section 6.1.10 for detailed description. It will be strongly recommended to all patients to use arm crutches during the entire trial and with a special importance until Day 4. The patients should only partly weight the sprained ankle when using crutches.

The study will start with the recruitment of the first patient. End of trial is defined as completion of the data base lock.

The study was originally planned to be started in Q1/2018. The first patient was screened on February 26th, 2018. The extended duration of the recruitment period will be approximately 35 months and will be completed when at least 808 eligible patients have been enrolled. (*revised per Amendment to protocol version 3.0*)

5.1.1. Study Schedule

The (planned) study schedule includes the following milestones:

| | |
|-----------------------------------|-----------------------|
| First patient first visit (FPFV): | February 2018 |
| Last patient last visit (LPLV): | December 2020 planned |
| Database hardlock: | Q1 2021 planned |

(*revised per Amendment to protocol version 3.0*)

Heel ensures that an end of trial notification will be submitted to the concerned Competent Regulatory Authorities and Independent Ethics Committees (IEC) according to regulatory requirements.

5.2. Discussion of Study Design

A multicentre, double-blind, randomised, active- and placebo-controlled, Phase III study is a well-established design and the duration of the treatment and follow-up period is appropriate. Patients are allowed to take rescue medication which protects also the placebo

patients. Using elastic bandages and semi-rigid braces ensures that all patients will receive the necessary mechanical support of the injured ankle.

5.3. Selection of Study Population

Patients with acute unilateral Grade 1 or Grade 2 sprain of the lateral ankle will be enrolled. Grade 3 patients are not eligible as for them topical gel treatment is not appropriate.

Ankle sprains are classified by 3 grades of sprains:

- Grade 1 sprain (mild): Slight stretching and some damage to the fibres (fibrils) of the ligament. The joint is stable.
- Grade 2 sprain (moderate): Partial tearing of the ligament. If the ankle joint is examined and moved in certain ways, abnormal looseness (laxity) of the ankle joint occurs. Clinically partial instability.
- Grade 3 sprain (severe): Complete tear of the ligament. If the investigator pulls or pushes on the ankle joint in certain movements, gross instability occurs. The joint is instable.

Fracture of the ankle should be excluded by using e.g. the Ottawa Ankle Rules. In case of any doubt the exclusion of fracture by x-ray should be considered as per standard of care. After excluding fracture the investigator will evaluate the stability of the ankle joint using the anterior drawer test, the inversion stress manoeuvre and the external rotation test.

The mechanism of the injury and the clinical symptoms (edema, hematoma, location of pain at palpation) will be documented to support the grading.

The high pain and swelling might influence the outcome of the grading at Day 1, therefore a confirmatory check of the grading will be performed at Day 4. Patients who are classified having Grade 3 ankle sprain after randomisation and up to Day 4 will be withdrawn from the study and their data will not be part of the efficacy analysis but will be part of the safety analysis.

The investigators will be trained during the investigator meeting to ensure a consistent assessment and grading between investigators.

5.3.1. Inclusion Criteria

Potential study patients must meet the following inclusion criteria:

1. Acute unilateral Grade 1 or Grade 2 sprain of the lateral ankle
2. ≥ 18 years of age
3. Legally competent male or female outpatient

-
4. Injury occurred within previous 24 hours before first treatment expected
 5. Signed Informed Consent
 6. After 5 minutes of rest, pain on passive movement by investigator measured by Visual Analog Scale (VAS) >50 mm
 7. Not pregnant (as proven by negative pregnancy test in case of woman of childbearing potential before first study drug administration) or breast-feeding. Females of childbearing potential must agree to maintain highly effective birth control throughout the study (see all details in section 9.6). Such methods include:
 - oral, intravaginal, transdermal combined (oestrogen and progestogen containing) hormonal contraception associated with inhibition of ovulation,
 - oral, injectable, implantable hormonal contraception associated with inhibition of ovulation, intrauterine device (IUD), intrauterine hormone-releasing system (IUS), bilateral tubal occlusion, vasectomized partner (if received medical assessment of the surgical success), sexual abstinence (only if defined as refraining from heterosexual intercourse during the entire period of trial participation).

5.3.2. Exclusion Criteria

Potential study patients will be excluded if at least one of the following exclusion criteria is present:

1. Similar injury affecting the same joint within the past 6 months
2. Bilateral ankle injury
3. Grade 3 ankle sprain
4. Fracture of the ankle (It should be excluded by using e.g. the Ottawa Ankle Rules. In case of any doubt the exclusion of fracture by x-ray should be considered as per standard of care)
5. Chronic joint disorders such as clinically relevant osteoarthritis or aseptic arthritis
6. Disorders that may lead to joint oedema for other reasons than ankle sprain (such as heart failure, thrombosis, lymphedema and others)
7. Diagnosis requiring bed rest, hospitalization, surgery, or use of any cast during the planned treatment period
8. Debilitating acute or chronic illness
9. Use of systemic and /or topical corticosteroids in the previous 8 weeks, any analgesics (e.g. paracetamol/ acetaminophen) in the previous 24 hours before

Screening Visit, or 48 hours in the case of long-acting NSAID, cyclooxygenase type 2 (COX-2) specific inhibitors, or tramadol and other opioids. Low dose acetylsalicylic acid (70 – 100 mg per day) for anti-thrombotic therapy is permitted if doses are stable for the month prior to Screening Visit and planned to be stable during the entire study

10. History of sensitivity to any component of the study drugs (including e.g. paracetamol/ acetaminophen intolerance; patients in whom asthma attacks, skin rash or acute rhinitis are triggered by acetylsalicylic acid or non-steroidal anti-inflammatory drugs (NSAIDs)
11. Unwilling or unable to comply with all the requirements of the study protocol
12. Concurrent injury to proximal structures in ipsilateral lower extremity (i.e. concurrent shin, knee, thigh, or hip injury)
13. History of ligament avulsion, fracture or surgery to the affected lower extremity
14. Presence of infections and/or skin diseases in the area of the study treatment site (including psoriasis)
15. Any previous treatments of the injured ankle, whether topical or systematic, are prohibited except RICE (simultaneous combination of all 4 elements Rest, Ice, Compression and Elevation, which is restricted to be used until starting treatment with the investigational drug)
16. Participation in any clinical study within the past 4 weeks
17. Any relationship of dependence with the sponsor or with the investigator.

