5.3.3. Discontinuation of Treatment

Patients who meet any of the discontinuation criteria will discontinue investigational treatment and will be followed up only for AEs until Day 14.

Study investigators may request the patient to discontinue investigational treatment in case of:

- Diagnosis of Grade 3 ankle sprain
- Any other medical condition requiring in the opinion of the investigator a change of the therapy for the baseline condition
- Occurrence of a medical condition requiring use of prohibited medications or treatment
- Medical condition affecting assessment of the primary endpoint
- Medical conditions affecting patient safety if the investigational therapy is continued: conditions and AEs causing safety concerns with investigational treatment to the ankle

joint area OR any other AE or condition that - in the opinion of the investigator – endangers patient safety if the investigational therapy is continued

- Lack of efficacy as considered by the investigator.

Discontinuation of investigational treatment and its reason will be documented in the medical records and recorded in the eCRF. If a patient discontinues investigational treatment, the discontinuation of treatment visit should be performed. Further treatment of the ankle sprain will be at discretion of the investigator and will not be recorded in the eCRF. In case the patient will be treated in another hospital or practice, the investigator will make efforts to collect and record AEs the patient might have had until Day 14. This can be done during an onsite visit or a phone call with the patient or with the treating physician at the other hospital or practice. Patients who discontinue prematurely from the study will not be replaced, except patients with Grade 3 sprain confirmed at any day up to Day 4 ('replacement' referring to the total number of patients to be enrolled, see also definitions in section 11.4).

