7.2.2. Randomization

- Patients who fulfil all the inclusion criteria and do not meet any of the exclusion criteria will be randomised to the investigational treatment and will receive Traumed[®] gel or diclofenac gel or placebo gel. (See section 6.1.2)
- The team member responsible exclusively for handling the study medication will dispense IMP to the patient, will apply the first dose and will train the patient how to use the dosage card and the IMP.
- The team member exclusively responsible for handling the study medication will train the patient how to use the elastic bandage and place the elastic bandage (soft support)
- Paracetamol (500 mg/tablet) will be dispensed as rescue medication for pain relief with a maximum dose of four tablets or 2000 mg/day, but not more than 2 tablets at a time. Patients are to be instructed to refrain from taking any analgesic medication other than the provided rescue medication and that they are not allowed to take paracetamol neither within 8 hours prior to visit 2. (For further visits the restriction will be 24 hours, consequently taking paracetamol will not be allowed within 24 hours prior to visit 3, visit 4 and visit 5).
- Patient diary will be distributed to the patient. The patient will be instructed to document the date, time and amount of paracetamol intake every day and to bring the diary to the site at each visit. In addition, the patient will be requested to document other concomitant medications in the diary and to record how many times he/she has applied the IMP on each day. The site staff will transfer the paracetamol consumption since last patient visit (including date, time, and amount of consumed tablets) and the IMP use from the diary into the eCRF.
- The patient will be strongly suggested to use arm crutches during the entire trial and with a special importance until Day 4

- Evaluation of any AEs experienced after informed consent has been signed, including AEs observed at the site of administration of the IMP (lateral ankle). SAE evaluation and reporting if applicable
- Patients will be instructed to return to the next visit (+/- 1 hour related to baseline assessment time) and return patient diary, IMP and remaining rescue medication

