According to the SmPC of Diclofenac Heumann Gel (HEUMANN PHARMA GMBH & CO. GENERICA KG, N., 2013) its use is contraindicated in case of sensitivity to any components of the gel (e.g. paracetamol, isopropanol, ethanol; see [protocol] section 6.1.1 for description of other ingredients), for patients in whom asthma attacks, skin rash or acute rhinitis are triggered by acetylsalicylic acid or NSAIDs, treatment for open wound, infections or inflammation of the skin (e.g. eczema) or application on the mucosa. Possible side effects are also described in the SmPC.

Diclofenac Heumann Gel is only recommended in first and second trimester of pregnancy if absolutely required. Systemic administration of diclofenac inhibited the ovulation in rabbits and the implantation and embryogenesis in rats. Teratogenicity was investigated in rats, cats and rabbits. Based on the available non-clinical data, diclofenac is considered non-teratogenic. (HEUMANN PHARMA GMBH & CO. GENERICA KG, N., 2013).

Placebo is contraindicated in case of sensitivity to any components of the gel, see [protocol] section 6.1.1 for description.

In the TAASS trial (Gonzalez et al. 2013) topical treatment with Traumeel® or diclofenac resulted in reduction of pain and restoration of function in patients with grade 1 or grade 2 ankle sprain. The current trial is designed to demonstrate the superior efficacy of Traumed® gel versus placebo and to assess the non-inferiority of Traumed® gel compared to diclofenac gel.

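### The protocol names open wound as a contraindication to the diclofenac gel, but no entry criterion excludes an untreated, uninfected open wound where the gel is applied

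*Protocol*

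**What the plan says.** Protocol section 3 (Introduction and Study Rationale) summarises the contraindications of the diclofenac gel. After sensitivity to a component, it names patients in whom asthma attacks, "skin rash or acute rhinitis are triggered by acetylsalicylic acid or NSAIDs, treatment for open wound", and goes on to skin infection or inflammation and mucosal use. SAP section 5.1 gives the same list without a page break: "treatment for open wound, infections or inflammation of the skin (e.g. eczema) or application on the mucosa".

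The entry rules are in protocol section 5.3.2, with copies in the protocol synopsis and in SAP section 6.1. Criterion 10 excludes sensitivity to a study-drug component, including "patients in whom asthma attacks, skin rash or acute rhinitis are triggered by acetylsalicylic acid or non-steroidal anti-inflammatory drugs". Criterion 14 excludes "Presence of infections and/or skin diseases in the area of the study treatment site (including psoriasis". Two other criteria come close to the subject: criterion 12, "Concurrent injury to proximal structures in ipsilateral lower extremity", and criterion 15, "Any previous treatments of the injured ankle, whether topical or systematic, are prohibited except RICE".

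Section 7.2.2 states the consequence of passing the list: "Patients who fulfil all the inclusion criteria and do not meet any of the exclusion criteria will be randomised to the investigational treatment". Section 6.1.3 has the gel rubbed over the injured area three times daily for 7 days and sets no condition that the skin be intact.

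**The concern.** The sponsor turned most of the comparator's contraindications into exclusion criteria and left one in the background text. Section 3 is not an eligibility rule. A site that follows section 5.3.2 to the letter may therefore enrol a patient with an open wound under the gel, and no eligibility violation is recorded. Because treatment is masked, the site cannot keep such a patient out of the diclofenac arm alone; only an entry criterion protects the patient before the first dose.

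What is at stake is patient safety and consistency within the protocol. Sample size, alpha, power and the between-arm comparison are not affected.

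**Working it through.** There is no figure in the plan to reproduce. The check sets the section 3 list against the entry criteria.

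| Contraindication in section 3 | Exclusion criterion |
|---|---|
| Sensitivity to a component | 10 |
| Asthma, rash or rhinitis triggered by acetylsalicylic acid or an NSAID | 10 |
| Open wound | none |
| Infection or inflammation of the skin | 14 |
| Use on mucosa | cannot arise at an ankle |

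Items that can apply at an ankle: 5 − 1 = 4. Carried over: 3 of 4. Open wound is named in 0 of 17 exclusion criteria and 0 of 7 inclusion criteria.

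**Could another criterion exclude the wound indirectly?**

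- Criterion 7 applies only if the diagnosis requires bed rest, hospitalisation, surgery or a cast.
- Criterion 12 concerns the shin, knee, thigh or hip, not the skin of the ankle.
- Criterion 13 concerns a history of avulsion, fracture or surgery.
- Criterion 14 catches an infected wound. Calling a fresh traumatic wound a skin disease is strained, and section 3 itself separates the two.
- Criterion 15 can catch a wound that has already been treated.

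An open wound that is untreated, uninfected and not in need of surgery passes all of these.

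**Does other text close the gap?**

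- The Day 1 physical examination in section 7.2.1 lists body systems, and skin is not among them. The signs recorded to support grading (section 5.3) are oedema, haematoma and the site of pain on palpation.
- Section 5.3.3 begins "Patients who meet any of the discontinuation criteria will discontinue investigational treatment", but its next sentence only permits the investigator to request this. One of its grounds is a safety concern about treating the ankle area, so it could stop treatment, but only after entry.
- Section 5.3.4 withdraws patients randomised in error, which requires a breached criterion. Here none is breached.

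**Chance of receiving the contraindicated product.** With the enlarged sample of section 11.4: 202 / (404 + 202 + 202) = 202/808 = 0.25.

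**The case against.** The best reply is that clinical judgement surrounds the written list. Section 7.2.1 has the investigator approach suitable outpatients, so judgement comes before the criteria check. Criterion 11 excludes patients who cannot comply, and a large wound might make gel plus an elastic bandage impractical. A dedicated team member applies the first dose and would see the skin. The injury described is an inversion sprain, and nothing in the documents suggests that open wounds are expected. These points make a case unlikely to slip through, but they rest on unwritten or indirect judgement, whereas other items from the same sentence were written down. Criterion 11 would not reach a small abrasion.

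It can also be said that open wound, like mucosa, concerns where the gel is put and could be handled by application instructions. That is a legitimate alternative, but the visible text contains no intact-skin instruction. Consent pages were removed from the public copy, so what patients were told is unknown.

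Three criticisms of the size stand. The count of 3 in 4 treats skin infection and inflammation as one item; split, it is 4 in 5, with the same item missing. The list is the protocol's paraphrase, not the label itself. The 25% is simply the allocation ratio and measures no risk without a frequency of wounds.

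**Conclusion.** The concern holds, as a minor point. Section 3 and the exclusion list are inconsistent on one contraindication that can apply at the treatment site, and the entry rules as written let an untreated, uninfected open wound through to blinded randomisation with a 1 in 4 chance of diclofenac gel. The gap is narrow. The number of patients affected cannot be estimated from the documents, and an attentive investigator would probably exclude such a patient anyway. The conclusion rests on the protocol's own summary of the label and on reading a fresh wound as something other than a skin disease.

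**What to change.** Insert *open wounds* at the head of criterion 14, before infections and skin diseases at the treatment site. Make the change in protocol section 5.3.2 and the synopsis, and carry it into the copy in SAP section 6.1.

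The item is checked within the existing Day 1 inclusion/exclusion check, so it needs no extra visit, procedure or eCRF field. It may add a few screening failures. A change to an entry criterion made during a trial would also need the approvals that section 1.4 sets for substantial amendments.

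SAP section 7 records the hard-lock transfer on 29 March 2021, so an amendment can no longer change who was enrolled here. The corrected wording belongs in any later protocol that uses this comparator.
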